3.0 Inclusion and Exclusion Criteria

PROTOCOL TITLE: Low InTensity Exercise intervention in PAD: The LITE Trial

3.1 Screening for eligibility.

Initial eligibility criteria will be assessed by telephone with a recruitment call script. Potential participants who remain eligible after the telephone screening will be scheduled for a baseline visit, where they will undergo additional testing to determine their eligibility for randomization.

- A. **Recruitment.** We will randomize 305 PAD participants over 32-months, allowing for a 15% drop-out at 52-week follow-up. This drop-out rate is comparable to the 52-week drop-out rate in our GOALS and SILC trials (52,55). We will identify participants using 1) Northwestern's Enterprise Data Warehouse to identify patients with PAD; 2) radio and newspaper advertising; and 3) bulk mailed postcards to people age 55 and older living in the Chicago area. We have successfully used each method in our prior clinical trials. Based on our previous work involving participants with PAD, we anticipate that the average age will be approximately 70 years, that at least 33% of participants will be minorities, and that approximately 50% will be women. For example, in our recently completed SILC randomized controlled clinical trial of exercise in patients with PAD (55), participants were average age 70.6 ± 10.3 and the average ABI was 0.61 ± 0.17 . In SILC, participants included 52% women and 45% African-Americans. In general, patients with PAD have a high prevalence of comorbid diseases, particularly coronary artery disease, cerebrovascular disease, and diabetes mellitus. Thus the patient population is likely to be of poorer health than that of similarly aged men and women without PAD in the general population.
- B. **Our experience successfully enrolling PAD participants in NHLBI-funded studies:** Since 2004, we have randomized 661 PAD participants from the Chicago-area into NHLBI-funded clinical trials. Since 1998, we have enrolled more than 1,800 participants with PAD into our NHLBI-funded studies. Thus, we have the experience and expertise to successfully recruit the proposed 305 PAD participants for the LITE Trial.
- C. **Randomization.** Participants will be randomized to one of three parallel arms using a SAS computer program. Block randomization will be implemented to ensure balance between the three groups. Randomization will be stratified by according to whether the participants are eligible for (and consented to) muscle biopsy.
- D. **Rationale for focus on walking exercise.** Walking exercise is the only form of exercise that consistently improves walking performance in PAD and is the only exercise currently recommended by practice guidelines for PAD (1,2,27,64).

3.2 Criteria.

Inclusion and exclusion criteria. All participants will have PAD. PAD will be defined as follows. First, an ABI ≤ 0.90 at the baseline study visit is a well-accepted standard for the diagnosis of PAD and will be an inclusion criterion (59-62). Second, people with an ABI of >0.90 and ≤ 1.00 who experience a 20% ankle systolic pressure drop after the heel-rise test will also be included. Third, potential participants with an ABI > 0.90 who have vascular lab evidence of PAD* or angiographic evidence of PAD** who have ischemic symptoms during the six-minute walk and/or treadmill exercise stress test will be eligible. In addition to meeting a criterion for PAD, all participants must be symptomatic, defined by one of the following criteria:; a) ischemic leg symptoms (primarily assessed with the San Diego Claudication

PROTOCOL TITLE: Low InTensity Exercise intervention in PAD: The LITE Trial

Questionnaire); b) report ischemic leg symptoms at the end of the six-minute walk; c) report ischemic leg symptoms at the end of the baseline treadmill stress test; d) walking impairment questionnaire results, e) interview with the potential participant about the presence and nature of leg symptoms during walking activity. Exclusion criteria are listed in Table 3.

* If the only criterion by which a participant is eligible to participate is a toe pressure, the toe pressure must be < 70 or the toe brachial index ratio must be < 0.60 if asymptomatic or < 0.70 if symptomatic.

** Angiographic criteria of PAD consist of a stenosis of 70% or greater in a lower extremity artery.

Table 3. Summary of exclusion criteria and justification for each criterion.

List of specific exclusion criteria	Justification for exclusion criteria
1. Above or below knee amputation, critical limb ischemia, wheelchair confinement, or foot ulcer.	1. Inability to fully participate in the intervention.
2. Individuals whose walking is limited by a condition other than PAD.	2. The intervention is designed to improve PAD-related walking impairment.
3. > Class II NYHA heart failure or angina. Increase in angina, angina at rest, or abnormal baseline treadmill stress test.	3. Exercise may not be safe for these potential participants.
4. Major surgery including lower extremity revascularization or orthopedic surgery during the prior three months or anticipated in the next twelve months.	4. Surgery may influence change in functional performance, independent of study interventions.
5. Major medical illness including renal disease requiring dialysis, lung disease requiring oxygen, or cancer (other than non-melanoma skin cancer) requiring treatment in the prior three years. Note: Potential participants may still qualify if they have had treatment for an early stage cancer in the past three years and the prognosis is excellent. Patients who use oxygen at night may still qualify.	5. These conditions may interfere with the ability to fully participate and complete the study.
6. Mini-mental status examination score <23 (63), dementia, or psychiatric illness including severe depression or anxiety. However, investigator discretion may be used to allow some people with an MMSE below this threshold to participate, if the investigator determines there is another reason for their lower score, including lack of sufficient familiarity with the English language or lack of sufficient education to achieve a score of 23 or higher. Note that the MMSE includes some spelling and English writing proficiency.	6. May interfere with ability to fully engage in the study.
7. Currently walking regularly for exercise at a level comparable to the amount of exercise prescribed in the intervention.	7. The interventions may not further improve functioning.
8. Currently enrolled in another clinical trial, exercise trial, or in cardiac rehabilitation. Currently enrolled in a clinical trial or participation in cardiac rehabilitation or a	8. Interference with ability to determine whether study interventions are responsible for improved outcomes.

PROTOCOL TITLE: Low InTensity Exercise intervention in PAD: The LITE Trial

trial of a therapeutic intervention within the past three months. For a clinical trial of a stem cell or gene therapy intervention, potential participants will be potentially eligible immediately after the final study visit for the clinical trial, so long as at least six months has passed since the participant received their final treatment in the stem cell or gene therapy intervention. For a clinical trial involving open-label therapy in which the treatment is not related to functional performance and will not change during the LITE Trial, participants may still qualify for the LITE Trial based on investigator discretion.

9. Individuals with PAD who have a history of lower extremity revascularization and currently have a normal ABI.

*10. Potential participants who are unable to walk for exercise at a sufficiently slow pace to avoid ischemic leg symptoms.**

9. We are seeking participants who currently have ischemia

10. Participants randomized into the low intensity intervention must be able to walk slowly enough to avoid ischemic leg symptoms.

**All individuals who are unable to walk for three minutes during a modified Gardner protocol or for one minute on a Gardner protocol exercise stress test will be interviewed by the study Principal Investigator (PI) or another physician investigator to determine whether they are able to walk sufficiently slowly to avoid ischemic leg symptoms during exercise activity.*

3.3 Special Populations.

Vulnerable populations (fetuses, pregnant women, children, prisoners, and institutionalized persons) and adults unable to consent will not be included in this study.

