Following final follow-up testing, participants may be called and asked to complete a questionnaire about their current walking activities. The trial demonstrated an important and unanticipated finding, that walking exercise that induced ischemic leg symptoms significantly improved walking ability more than walking exercise that did not induce ischemic leg symptoms. Despite its benefits, it was more difficult for participants to engage in high intensity exercise in this trial. In order to determine the long term effects of the intervention, we will ask study participants who completed the trial about their current exercise activity. Specifically, we will telephone individuals who have completed the study and ask them approximately five to ten minutes of questions about their current mobility, exercise activity, and physical activity. In addition to providing additional information about the exercise intervention, this information may be used to support a grant application. We will administer a verbal consent form prior to completing the study questionnaire. Only participants who agree via verbal consent will be asked the questionnaire.

9.2 Research procedures.

A. **Exercise intervention overview.** Drs. [name] and [name], internationally recognized experts in behavior change, will direct the exercise interventions in the LITE Trial. Their expertise is complementary. [name] has specific expertise promoting exercise for patients with chronic health conditions (43,44,65,66). [name] has specific expertise in telephone-delivered behavioral interventions for diet and activity change that incorporate mobile technology. She pioneered the use of mobile transmission of participants' behavioral data to telephone coaches in behavioral intervention trials (67). This connective approach to behavioral interventions enables the coach to offer responsive, highly tailored interventions efficiently and allows participants to feel supported but also held accountable and avoids the need for regular visits to the exercise center.

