11.0 Data and Specimen Management

11.1 Data analysis plan.

- A. **Data management.** We will use data management methods in place for our ongoing NHBLI-funded PAD studies. Data from baseline and follow-up study visits are acquired on paper forms and processed using the Teleform system by Cardiff Software. We have successfully used this system for over 8,000 patient visits in our previous and ongoing studies. Data are backed-up on multiple hard drives and copied to CDROM for secure off-site storage.
- B. **Data Safety Monitoring Board (DSMB).** We have identified nationally recognized experts to serve on the DSMB.

Statistical Analyses. Analyses will be performed according to the intention to treat principle. Data will be analyzed according to each participant's originally assigned group, irrespective of whether the participant adheres to his/her assignment. Prior to analyses, the distributions of the variables (changes) will be examined and necessary transformations will be performed. The balance of socio-demographic factors and prognostic factors (such as age, sex, race, ABI, comorbidities, and relevant medication use) will be compared between the three groups using ANOVA or chi-square tests. If there is any indication of major imbalance, proper analysis of covariance adjustments will be performed in data analyses.

NOTE: The original plan to use two sample two-tailed t-tests was changed to a mixed model for repeated measures analysis on 8/27/2020 prior to analyzing any data. This change was made because as of 8/27/202, investigators are projecting an approximately 16% loss to follow-up rate at 52 week follow-up. The mixed model for repeated measures will be used to adjust for missing data.

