For our Primary Aim, we will use mixed model for repeated measures (MMRM) analysis to compare changes in six-minute walk performance at 52-week follow-up between the low vs. the high-intensity exercise group and between the low-intensity exercise group vs. the control group, respectively. To this end, the 26-week and 52-week changes of six-minute walk from baseline are treated as correlated outcomes, and independent variables include visit (26-week and 52 week), treatment (low-intensity, high-intensity, control), visit/treatment interactions and baseline six-minute walk performance. Unstructured variance-covariance matrix will be used to model the within-person correlations. In addition, we will also adjust for potentially imbalanced baseline confounders such as age, sex and baseline six-minute walk performance. When there is evidence that the normality assumption for the distribution of measures of interest is severely violated, we will perform Wilcoxon rank-sum test for the comparison. The nonparametric adjustment for the imbalance in mean difference of baseline covariates will be employed, when needed.

PROTOCOL TITLE: Low InTensity Exercise intervention in PAD: The LITE Trial

For Secondary Aim #1, we will use MMRM analysis to compare changes in six-minute walk, physical activity, and SF-36 PF and WIQ distance and speed scores at 26-week follow-up between the low- and high-intensity exercise groups and between the low-intensity exercise and control group, respectively.

For our Secondary Aim #2, we will use MMRM analysis to compare changes in maximal treadmill walking time, physical activity, and SF-36 PF and WIQ distance and speed scores at 52-week follow-up between the low- and high-intensity exercise groups and between the low-intensity exercise and control groups, respectively.

For our Secondary Aim #3, we will use normal approximation for binomial distribution to compare the proportion of participants who achieve adherence (as defined in section C18) between the low vs. high intensity exercise groups. We will also use logistic regression to compare the adherence rate between these two groups, adjusting for potentially imbalanced baseline confounders such as age, sex, and baseline six-minute walk performance. We will also use two sample two-tailed t-tests to compare adherence to the exercise intervention overall and at the prescribed intensity between the high vs. low intensity groups at 52-week follow-up.

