For our Secondary Aim #4, we will use MMRM analysis to compare changes in six-minute walk distance, physical activity, and SF-36 PF and WIQ distance and speed scores at 26-week follow-up between the high-intensity exercise and control groups.

For our Secondary Aim #5, we will use MMRM analysis to compare changes in six-minute walk distance, maximum treadmill walking time, physical activity, and SF-36 PF and WIQ distance and speed scores at 52 week follow up between high intensity exercise and control groups.

For our Secondary Aim #6, we will use two sample two-tailed t-tests to compare changes in COX, citrate synthase, and mitochondrial DNA at 52-week follow-up between the low intensity vs. the high-intensity exercise group and between the low-intensity exercise and control groups. We will also compare change in nitrotyrosine muscle measurements between the high-intensity exercise and the control groups. We will repeat these comparisons for the participants who adhere to their prescribed exercise intensity, measured by the ActiGraph.

For our Exploratory Aim #1, we will use two sample two-tailed test compare patients' perception to exercise at 52-week follow-up between high and low-intensity groups. For our Exploratory Aim #2, we will evaluate the effect of modified combo intervention (weight loss + LITE home-based exercise) on six-minute walk distance at approximately 12 week follow-up. This pilot study was completed in 2018.

The significance level for the Primary Aim will be 0.05/2 to adjust for two comparisons between low-intensity and high-intensity arms and between low-intensity and control arms.

The significance level will be 0.05 for all secondary aims. Furthermore, Secondary Aims #4 and #5 were pre-specified but added after the LITE Trial was underway in response to two negative trials of home-based exercise in patients with PAD demonstrating that a high-intensity walking exercise program did not improve six-minute walk or other outcomes in people with PAD (5, 6).

PROTOCOL TITLE: Low InTensity Exercise intervention in PAD: The LITE Trial

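### Randomisation is stratified by muscle-biopsy eligibility and consent, but no planned mixed model names that factor and the within-stratum allocation ratio is not stated (minor)

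*Combined protocol and SAP*

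**What the plan says.** Section 3.1 C (Randomization) gives one stratification factor: "Randomization will be stratified by according to whether the participants are eligible for (and consented to) muscle biopsy". It also says "Block randomization will be implemented to ensure balance between the three groups". It gives neither the block size nor the ratio within each stratum. Section 11.2 gives one overall allocation: 120 low intensity, 120 high intensity, 65 control.

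For the primary MMRM, Section 11.1 states that "independent variables include visit (26-week and 52 week), treatment (low-intensity, high-intensity, control), visit/treatment interactions and baseline six-minute walk performance". It then adds that "we will also adjust for potentially imbalanced baseline confounders such as age, sex and baseline six-minute walk performance". A general rule earlier in the same section reads: "If there is any indication of major imbalance, proper analysis of covariance adjustments will be performed in data analyses". Its examples of factors to check are age, sex, race, ABI, comorbidities and medication. Neither statement gives a threshold or names the biopsy stratum.

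For Secondary Aims #1, #2, #4 and #5 the section names the method and the outcomes only, for example "we will use MMRM analysis to compare changes in six-minute walk distance, maximum treadmill walking time, physical activity". No covariates are listed.

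**The concern.** A factor that constrains the randomisation normally belongs in the model whatever the observed balance. Here it could enter only through a rule driven by observed imbalance. Blocking within strata at a common ratio is meant to prevent imbalance on this factor, so the rule would not be expected to pick it up.

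What is at stake depends on the unstated within-stratum ratio. With a common ratio, omission costs a little efficiency. With different ratios, stratum is associated with arm. Any stratum difference in walk change that remains after adjustment for baseline walk then enters the comparisons with control: one of the two primary comparisons, and Secondary Aims #4 and #5. The question is fair because the plan wants 50 biopsied participants in every arm, which is 50/65 = 77% of controls but 50/120 = 42% of each exercise arm.

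**Working it through.** **Inputs from the documents.** 120/120/65 randomised; 15% drop-out; SD of change 60 m; two-sided 0.025 per primary comparison; detectable differences 0.43 SD and 0.52 SD (Section 11.2). Section 11.1 says "investigators are projecting an approximately 16% loss to follow-up rate at 52 week follow-up".

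**Assumed, because the documents give no value.** The stratum difference g in walk change left after baseline-walk adjustment (10, 20 or 30 m), the share of participants in the biopsy stratum, and the within-stratum ratio. The 60 m is used as the residual SD.

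**1. The plan's own figure.** Completers are 120 × 0.85 = 102 and 65 × 0.85 = 55.25. The standard error (SE) for low versus control is √(1/102 + 1/55.25) = 0.1670 SD, or 10.02 m. Noncentral-t power at 0.52 SD (31.2 m) is 80.1%; for low versus high at 0.43 SD it is 79.1%. Both reproduce the stated 80% to rounding.

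**2. Same ratio in both strata, stratum omitted.** Arm and stratum are unrelated, so bias is 0. The estimated variance is inflated by r = p(1−p)g²/60², where p is the biopsy share. Type I error is 2[1 − Φ(2.2414√(1+r))].

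| g | r at p = 0.60 | type I error |
|---|---|---|
| 10 m | 0.0067 | 0.0245 |
| 20 m | 0.0267 | 0.0231 |
| 30 m | 0.0600 | 0.0210 |

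Power at 0.52 SD, normal scale: 0.52/0.1670 = 3.113. With the term it is Φ(3.113 − 2.2414) = 80.8%. Without it, g = 20 m, it is Φ(3.113 − 2.2711) = 80.0%.

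Reaching 50 controls at the overall ratio needs p = 50/65 = 0.769, about 235 of 305 participants. At g = 20 m, r is then 0.769 × 0.231 × 400/3600 = 0.0197, so the effect is smaller still.

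A simulation of the planned MMRM agrees (20,000 runs per case; p = 0.60; 16% missing at 52 weeks; assumed 10% missing at 26 weeks, visit correlation 0.6, baseline SD 100 m, baseline-change correlation −0.2). At 10/20/30 m type I error was 0.023/0.024/0.021. The SE was 9.65/9.74/9.90 m, against 9.62 m with the term. Power at 31.2 m for g = 20 m was 83.2%, against 83.9% with the term.

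**3. Illustration only: biopsy stratum 50/50/50, remainder 70/70/15, stratum omitted and imbalance rule not applied.** The share difference is 0.769 − 0.417 = 0.353, so low versus control and high versus control each shift by 0.353g in size. Low versus high has equal shares and does not shift.

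| g | shift | type I error, simulated MMRM |
|---|---|---|
| 10 m | 3.5 m | 0.035 |
| 20 m | 7.1 m | 0.061 |
| 30 m | 10.6 m | 0.116 |

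Hand check at 20 m: 0.353 × 20 = 7.05 m, and 7.05/10.02 = 0.703. The pooled within-arm stratum variance is (2 × 120 × 0.417 × 0.583 + 65 × 0.769 × 0.231)/305 = 0.229, so r = 0.229 × 400/3600 = 0.0255 and the critical value is 2.2414√1.0255 = 2.270. Type I error is Φ(−1.566) + Φ(−2.973) = 0.060. With the stratum in the model the simulated error was 0.025 to 0.027. A stratum gap acting only through baseline walk (100 m) is already removed by the planned model: bias 0.05 m, type I error 0.027.

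**4. Price of the term in the illustration.** The added variance is 0.353²/(0.85 × 69.87) = 0.00209, on top of 0.02790, a factor of 1.075. Power at 0.52 SD falls from 80.1% to 76.9%, and the detectable difference becomes 0.538 × 60 = 32.3 m.

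**The case against.** The strongest reply is that nothing material follows from the allocation the documents state. At 120:120:65 in both strata the omission is unbiased, slightly conservative and costs less than a point of power for a 20 m stratum difference. That stands.

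A reader might infer that 50 biopsies per arm implies a 1:1:1 biopsy stratum, and so that the control comparisons are biased. The documents do not support this. The power section and the payment section (22.4) both describe random selection for biopsy, and the latter places it after the participant agrees. That reads more naturally as choosing 50 per arm among consenters than as a changed ratio. The biopsied subset is also not the stratum, which is defined by eligibility and consent. Stratum differences of 20 to 30 m after baseline adjustment have no documentary basis either; 30 m is the size the protocol calls a small meaningful change.

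A reader might also infer that the plan could never adjust for the factor. Its lists of covariates are open, and a split of 77% against 42% could well be judged a major imbalance. What survives is that this rests on judgement, with no threshold and no mention of the factor.

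Finally, the secondary models do not single this factor out for omission; they list no covariates at all. Secondary Aim #6 uses t-tests within the biopsied subset, where the stratum is constant, so the point does not apply there.

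**Conclusion.** The concern holds as a minor gap in specification. The stratification factor is absent from the primary MMRM, the secondary MMRMs have no stated covariates, and the fallback is an imbalance rule without a threshold. If the stated allocation holds in both strata, there is no bias, and type I error is about 0.02 to 0.025 at a nominal 0.025. The figures that show harm (shifts of 3.5 to 10.6 m, type I error up to 0.116) need three things together: a different ratio in the biopsy stratum, a stratum difference that baseline walk does not explain, and the imbalance rule left unused. No document establishes any of the three, so these figures show why the ratio should be stated and are not evidence that the trial's results are biased. Low versus high intensity is unaffected in either case.

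**What to change.** 1. Include biopsy stratum (yes/no) as a fixed effect in the primary and secondary MMRMs whatever the observed balance, and list the covariates of the secondary models. Add stratum-by-visit for outcomes measured at both 26 and 52 weeks. In the illustration, with a gap of 10 m at 26 weeks and 20 m at 52 weeks, a main effect alone leaves 1.8 of 7.0 m of bias; stratum-by-visit leaves 0.1 m.
2. State the allocation ratio used within each stratum.
3. Section 9.1 already reports that "The trial demonstrated an important and unanticipated finding, that walking exercise that induced ischemic leg symptoms significantly improved walking ability". The stratum-adjusted analysis should therefore be labelled as added and reported beside the planned model, not put in its place.

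The cost is one covariate already recorded at randomisation and a few lines of text. With a common ratio no precision is lost (SE 9.62 m with the term, against 9.65 to 9.90 m without). If the biopsy stratum was in fact 1:1:1, low-versus-control power at 0.52 SD falls from about 80% to 77%, the detectable difference rises from 31 m to about 32 m, and the power statement should be restated.
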